This pilot study intends to address the **critical unmet need** to develop novel treatments for AUD, such as rTMS, that directly impact *drinking behavior*. Binge drinking and high intensity drinking, or consumption meeting *at least* binge criteria, is a high-risk alcohol self-administration (ASA) pattern associated with the binge-intoxication stage of AUD and the rewarding effects of alcohol. We propose to quantify the impact of mPFC rTMS on ASA using our novel "rate-control" paradigm. The rate control paradigm allows subjects to determine how quickly their breath alcohol concentration (BrAC) will change (increase, decrease, or stay the same) over the next 3-5 minute epoch, at the end of which brief computer-assisted assay of craving for alcohol and subjective response attributed to alcohol's effect on stimulation, sedation, liking and well-being in a manner comparable to the Brief BAES^{38,39}. Each assay requires less than 20 seconds to complete and will be administered during the last ~0.5 minutes of alcohol delivery but before selection of the next rate of exposure. The ensemble provides detailed self-administered time course of alcohol exposure and corresponding time-stamped series of quantified perceptions for analysis. This approach has demonstrated sensitivity in associating self-reported high intensity drinking and the time until a binge alcohol exposure of 80 mg/dL (Figure 1).

Our premise is that clinically impactful neuromodulation should change ASA. Coupling rTMS to a laboratory-assessed ASA paradigm could document *causal* changes in drinking behavior attributable to modulation of specific neural circuits. The **goal of this project** is to generate preliminary data supporting our **central hypothesis** - rTMS targeting to the mPFC, a primary cortical input to the FSR circuit, will decrease the rate of alcohol self-administration.

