2.0 Objective(s)

Primary Objective

The **primary objective** of this pilot study is to determine the effect size of the relationship between mPFC LF rTMS and a change in the time required to self-administer at least a binge-level alcohol exposure of 80 mg/dL. We hypothesize that,

[figure not shown]

Figure 1: High Intensity Drinking Groups and Time to 80 mg/dL. N=33 subjects completing the rate control ASA paradigm. Groups are defined by multiples of self-reported binge intensity for display. Time to 80 mg/dL is sensitive to drinking intensity ($p = 0.0035$). Report in preparation.

compared to sham stimulation, mPFC LF rTMS will slow the time to a breath alcohol concentration (BrAC) of 80 mg/dL.

Secondary Objective

The **secondary objective** is to explore the effects of mPFC rTMS on subjective responses to alcohol, time until a high intensity drinking exposure, and, during a 4-week follow-up period, self-reported alcohol consumption patterns.

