targeting the mPFC, delivered over FP1 per the 10-20 international scalp electrode location system (an approach taken by our consultant^{41,42}), within the following stimulation parameters: Continuous 20-minute train of 1 Hz rTMS, at 110% of MT, for a total of 1200 pulses. This protocol was shown by Chen et al. (2013) to produce an inhibitory effect on local cortical excitability as well as effects on connectivity of related circuitry³³. The stimulation design is within safety limits for rTMS^{32,40,43}. If needed for tolerability, stimulation intensity (% MT) may be decreased, down to but not beyond the subjects resting MT, during the course of the study section.

rTMS administration monitoring

All subjects will be instructed to wear earplugs during each rTMS session and will be monitored by medically trained research staff throughout the entirety of each rTMS session.

Subjects will complete the rate control IV alcohol self-administration session as soon as feasible after rTMS administration. Upon completion of the alcohol self-administration session, subjects be taken to the ICRC for post-session monitoring until the time for discharge.

Alcohol Administration

Laboratory Testing: Each subject will be tested during each of two outpatient visits spanning Goodman Hall and University Hospital. After testing is complete, subjects will remain at the ICRC until at least 7 pm or their BrAC reaches 35 mg/dL, whichever is later.

Preparation for Testing: Using sterile technique, a 20 gauge (or 22 gauge if necessary) indwelling venous catheter will be placed in an antecubital vein by an ICRC nurse, then flushed with saline and capped with a heparin lock. The subject will be instructed in the use of the Draeger® BrAC meter and familiarized with the subjective response procedures under NSL technician supervision.

Preparation for Infusion: After the subject is prompted for a bathroom break, the venous catheter will be Y-connected to 2 parallel infusion pumps, each capable of delivering up to 999 ml/hr and set to deliver 4 ml/hr to keep the vein open. Subject concerns of any kind will be addressed, and the start of the infusion, marking the beginning of experimental time, $T_{xp} = 0$, will be announced. Subjects will be unaware of BrAC readings and infusion rates at all times. The subject will be able to talk to the technician at any time without manual effort.

Infusion rate profile computation:

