Using individualized PBPK parameters⁴⁴, the Computer-assisted Alcohol Infusion Software⁴⁵⁻⁴⁸ will deliver an approximately 6.0 % (v/v) alcohol solution prepared by the Research Pharmacy. The infusion rate profile is based on individualized physiologically-based pharmacokinetic model parameters to achieve specified incremental alcohol exposure rates independent of the subject's age, height weight and gender. The safety limit will be set to 170 mg/dL, but subject inputs that would exceed 165 mg/dL are

disabled, allowing subjects to self-administer to a high-intensity drinking threshold of 160 mg/dL if they so choose and accommodating potential deviance from our pharmacokinetic modelling or measurement error.

We will use the rate control paradigm during the 90-minute alcohol self-administration session to allow the subject to determine their alcohol exposure trajectory (Figure 3). For the first self-administration epoch and at the end of each subsequent 3-5 min self-administration interval, the subject will specify the next alcohol exposure rate. Alcohol delivery raises the subject's BrAC by the specified rate over 3-5 minutes. During the last ~0.5 minutes of the exposure, the subject may complete the brief computer-assisted assay of craving for alcohol and subjective response and then select the next exposure rate, all while the current exposure rate is maintained.

[figure not shown]

Figure 3: Exposure Rate Selection and Subjective Response Determination Sequence. The task begins with an initial exposure rate selection, with the display indicating no past rate of change (baseline). After 2.5 minutes, a set of subjective responses are collected over approximately 20 sec after which time the next exposure rate selection prompt is displayed, now indicating the prior selection in the left hand (shaded) portion of the display. The choice and subjective response sequence is repeated throughout the experiment. The next exposure rate is then selected by rotation of the CAIS response button (Griffin Technologies Powermate®, inset) to a position within the available range depicted in gray. The arrow position follows button rotation in real time, and rate chosen by single button press. Text instructions are for illustrative purposes.

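### No craving or subjective-response reading is specified between stimulation and alcohol, so separating a resting rTMS effect from a changed response to alcohol would rest on extrapolation

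*Combined protocol and SAP*

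**What the plan says.** Section 2.0 sets the secondary objective, in part, to "explore the effects of mPFC rTMS on subjective responses to alcohol". Section 3.0 defines the matching outcome as the responses during the self-administration sessions and does not define a change from baseline.

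Section 7.0 gives the order of a session: cue-recall questions about a recent drinking experience, 20 minutes of 1 Hz rTMS or sham, then the infusion as soon as feasible. For the task itself the documents say:

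- Figure 3 caption: "The task begins with an initial exposure rate selection, with the display indicating no past rate of change (baseline"). The word in parentheses describes the rate display, not a rating.
- Same caption, next step: "After 2.5 minutes, a set of subjective responses are collected over approximately 20 sec".
- Infusion rate profile computation: "Alcohol delivery raises the subject's BrAC by the specified rate over 3-5 minutes", and "During the last ~0.5 minutes of the exposure, the subject may complete the brief computer-assisted assay of craving for alcohol and subjective response".
- Section 1.0: the assay "will be administered during the last ~0.5 minutes of alcohol delivery but before selection of the next rate of exposure".

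Before the infusion, the only contact with the assay is that the subject is "familiarized with the subjective response procedures under NSL technician supervision" (Section 7.0, Preparation for Testing). Section 12.0 describes a Cox model for time to exposure and states no analysis for the subjective responses.

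**The concern.** A response to alcohol is naturally read as a change from the subject's state without alcohol on the same day. Every rating the protocol describes is taken on alcohol, after priming and after stimulation.

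The protocol's own rationale (Sections 1.0 and 7.0) is that stimulation of this region can change craving, and subjects are cued to think about drinking before and during stimulation. A difference in craving that exists before any alcohol is delivered is therefore an expected pathway. If active rTMS gives lower craving ratings during the infusion, two explanations compete: craving was already lower at zero BrAC, or alcohol had a different effect on it. They would lead to different hypotheses for the larger study that this pilot is meant to inform, and the planned readings do not observe the point at which they differ.

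**Working it through.** **1. Is a pre-alcohol reading specified anywhere?** The candidates are:

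- Cue-recall questions (Section 7.0, rTMS Treatment): before stimulation, described as priming, with no score mentioned.
- Familiarization (Section 7.0, Preparation for Testing): before the infusion, with no recorded value mentioned.
- PACS and Subjective Response Questions (Section 7.0, Recruitment and Screening): interview measures, some or all completed at discretion. The calendar marks PACS at the interview only.
- Subjective Measures row (Section 9.0): read as marked at both experimental visits and follow-up, with no timing within the day.

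None schedules a recorded reading between stimulation and the start of infusion, or before stimulation on the session day.

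**2. Time of the first assay.** First assay = epoch length minus about 0.5 min.

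- 3-minute epoch: 3 - 0.5 = 2.5 min, which reproduces the Figure 3 caption.
- 5-minute epoch: 5 - 0.5 = 4.5 min.

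**3. BrAC at the first assay.** The documents give no range of exposure rates. Assume a constant rate reaching 80 mg/dL at time T, so BrAC = (80/T) × t. For example, T = 20 and t = 2.5 gives 4 × 2.5 = 10 mg/dL. The table shows T = 20, 45 and 90 min. At T = 10 min the values would be 8 × 2.5 = 20 and 8 × 4.5 = 36 mg/dL. The first reading is thus at low but usually non-zero BrAC, and since the rate is chosen after stimulation it can differ by condition.

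**4. How well can zero BrAC be inferred from the on-alcohol series?** Assume, per session, a straight line of rating on BrAC, independent residuals, and BrAC held at 80 mg/dL once reached. In residual-SD units, with b the BrAC values at the n assays,

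SE(intercept) = sqrt(1/n + mean(b)² / Σ(b - mean(b))²).

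Example with 3-minute epochs and T = 20. There are n = 90/3 = 30 assays, with BrAC 10, 22, 34, 46, 58, 70 and then 24 values of 80. The mean is 2160/30 = 72 and the sum of squares about the mean is 10,200. SE = sqrt(1/30 + 5184/10,200) = 0.736. Adding one reading at zero gives n = 31, mean 69.68, sum of squares 15,217, and SE = sqrt(1/31 + 4855/15,217) = 0.593.

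| Epoch (min) | T (min) | BrAC at first assay (mg/dL) | Intercept SE, as specified | With a reading at zero | Reduction |
|---|---|---|---|---|---|
| 3 | 20 | 10 | 0.736 | 0.593 | 19% |
| 3 | 45 | 4.4 | 0.479 | 0.432 | 10% |
| 3 | 90 | 2.2 | 0.371 | 0.348 | 6% |
| 5 | 20 | 18 | 1.039 | 0.721 | 31% |
| 5 | 45 | 8 | 0.642 | 0.540 | 16% |
| 5 | 90 | 4 | 0.488 | 0.438 | 10% |

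Reduction = 1 - (with / as specified). As specified, the intercept and slope estimates correlate between -0.87 and -0.97, so an error in one is largely taken up by the other.

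The last column understates the main benefit and should not be the argument for the change. A single reading at zero has an SE of 1 in these units, so if the straight line were exactly right it would often be less precise than the extrapolated intercept. Its value is that it needs no assumption about the shape of the curve below the first on-alcohol reading.

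**5. What would a pre-stimulation reading add?** Precision only. With 20 × (1 - 0.30) = 14 completers, 7 per sequence, adjusting session differences for one covariate gives an expected variance factor of (1 - ρ²)(1 + 1/10), where ρ is the assumed correlation between session differences in baseline and in outcome:

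- ρ = 0.3: sqrt(0.91 × 1.1) = 1.00, about 0% reduction in SE.
- ρ = 0.5: sqrt(0.75 × 1.1) = 0.91, about 9%.
- ρ = 0.7: sqrt(0.51 × 1.1) = 0.75, about 25%.

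**The case against.** The strongest defence is that the protocol promises only to explore effects on ratings during the sessions. It claims no mechanism. For that purpose the randomized crossover is sound: the active-sham contrast estimates the total effect of stimulation on the ratings, priming is common to both conditions, and day-to-day variation is noise that randomization balances on average. Section 1.0 also promises a time-stamped series of ratings alongside the exposure curve, so a condition effect on level can be modelled apart from a condition-by-BrAC slope. For slow starters the first reading is close to zero BrAC. All of this stands.

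Several stronger readings are tempting and are not supported:

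- That the sessions have no baseline. The documents only fail to specify one. Familiarization precedes the infusion and its responses may be kept, the calendar row is untimed, and the Figure 3 image was not available.
- That the two effects cannot be separated. They can be, by a model. The weakness is that the model extrapolates over exposure chosen after stimulation, is confounded with time, and is not planned.
- That a pre-stimulation reading would solve the problem. It cannot separate a resting shift from a response to alcohol.
- That the precision gain from a pre-stimulation reading is 5%, 13% or 29% at ρ = 0.3, 0.5 or 0.7. That is the large-sample formula 1 - sqrt(1 - ρ²), which ignores the cost of estimating the covariate slope with 14 completers.

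What the defence does not answer is that the stated objective concerns the response to alcohol, and the reading needed to interpret it that way is missing from the schedule.

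**Conclusion.** The point holds in a limited form. The protocol specifies no craving or subjective-response reading after stimulation and before alcohol. The first described rating comes 2.5 to 4.5 minutes into a self-chosen exposure, at an assumed 2 to 18 mg/dL for constant rates reaching 80 mg/dL in 20 to 90 minutes. Attributing an active-sham difference to a changed response to alcohol, as opposed to a resting shift, would then depend on extrapolation to zero BrAC.

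The total contrast of on-alcohol ratings is valid, and time to 80 mg/dL, the sample size and the Cox analysis are untouched. A reader might infer that the secondary outcome is biased or uninterpretable; the documents do not support that. The BrAC and SE figures rest on assumed rates, a straight-line model and independent residuals. The finding that no reading is scheduled rests on the text alone.

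This is an inexpensive improvement to an exploratory secondary outcome. It merits action because a zero-alcohol reading not taken on the day cannot be reconstructed.

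**What to change.** If a post-stimulation, pre-infusion reading is already taken, for example at familiarization, state its timing and how it enters the analysis. Otherwise:

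1. In Section 7.0 and the Section 9.0 calendar, add the same assay in both sessions after stimulation and before the first rate selection, at experimental time zero.
2. In Section 12.0, report the rTMS-sham difference at that reading as the pre-alcohol effect. Analyse subjective response to alcohol relative to it, alongside the total on-alcohol contrast. Because the reading follows stimulation, it should not be used as an ordinary baseline covariate for the total effect.
3. State how BrAC enters the analysis of response to alcohol. The new reading fixes the starting level, but exposure after that is still chosen by the subject and may differ by condition.
4. Optionally, add one reading before the cue-recall questions as a session-baseline covariate, for precision only.

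Section 1.0 says of the assay: "Each assay requires less than 20 seconds to complete and will be administered during the last ~0.5 minutes of alcohol delivery". One or two extra ratings therefore cost under a minute per session on the existing software, plus protocol and calendar wording. The downside is one or two additional brief ratings, identical in both conditions.

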8.0 Reportable Events

Serious adverse events resulting in any physical harm associated with testing will be reported to the IRB within 24 hours; minor adverse events (e.g. nausea, infusate infiltration, discomfort associated with infusion) will be reported to the Alcohol Studies DSMB meeting at least annually.

Adverse events (AEs), especially those for which the relationship to study treatment is not “unrelated,” will be followed up until they have returned to baseline status or stabilized at the discretion of the PI. If after the follow-up period, return to baseline or stabilization cannot be established an explanation will be recorded in the source documentation.

9.0 Study Calendar

rTMS Study	Screening		Experimental Visits		Follow-up
Procedure	Phone	Interview	Usual 1	Usual 2	1
Phone Screen	X				
Informed Consent		X			
Audit		X			
SSAGA		X			
SKID V		X			
UPPS-P		X			
SRE		X			
PHQ-9		X			
SIP-r		X			
Medical History		X			
Nicotine History Measure		X			
Five Factor Model Form		X			
APT		X			
PACS		X			
TLFB		X	X	X	X
CIWA		X			
GAD-7		X			
UDS		X	X	X	
UPS		X	X	X	
BrAC			X	X	
Liver Function		X			
Genotype Sampling		X			
rTMS			X	X	
Alcohol Exposure			X	X	
Subjective Measures			X	X	X
CAGE		X			
General Self-Efficacy Scale		X			
DRSEQ-R		X			
AEQ		X			
DMQ		X			
TMS Screening Checklist		X			

10.0 Data Safety Monitoring

The Data Safety and Monitoring Board (DSMB) that monitors virtually all the alcohol studies at IUSM, chaired by [name], who is independent of the sponsor and investigators, and comprised of other faculty with like status, will review this study at six-month intervals. The following will be monitored as part of the Data Safety Monitoring Plan (DSMP): data quality, subject recruitment, accrual, retention, outcome and adverse event data, assessment of scientific reports or therapeutic development, results of related studies that may impact subject safety, and procedures designed to protect the privacy of subjects.

The IRB is notified of significant findings by way of the DSMB meeting minutes at the time of continuing review. Due to the small sample size and single site design of this protocol, there is not sufficient justification for conducting interim analyses to examine trends. Data on the number of subjects enrolled and the number of adverse events will be reviewed by the DSMB every six months and more frequently if needed. The resultant report will be issued to the Indiana University IRB at least at the time of continuing review or more frequently by request. Any unanticipated events will be immediately directed to the PI who will follow the Indiana University IRB reporting procedures.

11.0 Study Withdrawal/Discontinuation

The participant may withdraw from the study at any time for any reason, and will be paid an amount pro-rated to the duration of their participation on the testing day, including time to recover to a BrAC < 35 mg/dL. The PI may choose to terminate any subject's participation at any time if it is deemed that s/he cannot participate or cooperate in testing procedures safely, with the same pro-rated compensation to the subject.

12.0 Statistical Considerations

Analyses

Sample Size

We plan to consent and screen 30 subjects, enroll 20 subjects and anticipate a 30% drop out rate, yielding 14 completers. This is consistent with our previous clinical trial efforts, including a study of adjunct rTMS for cognitive impairment in first-episode psychosis³⁷.

Statistical and Power Analyses

We will conduct a Cox proportional hazards survival analysis, which will control for drinking intensity, to determine effect sizes for a subsequent, properly powered formal study of the effect of rTMS on rate control alcohol self-administration. A recent review reported Cohen's d from 0.05 to 4.42 of rTMS on craving and other substance use disorder related outcomes⁵⁰. Our previous alcohol self-administration work showed effect sizes from 0.49 to 1.31 depending on the phenotype. Thus, overall, we hope for an effect size of at least 0.5 across SA1 and SA2.

Finally, with consent, we are collecting blood samples to allow for the combination of data from this project with previously collected human samples; enabling future analysis of polygenic risk in the combined sample.

13.0 Statistical Data Management

Primary data will be collected via paper source documents, phone interviews, and direct data capture from clinical and symptom measurements. Data will be stored electronically on a department server and paper source documents will be stored in a double locked and access-controlled research records room. The storage location will be backed up automatically on a daily basis. Other data sources include pathology lab data and Scram systems data that will be stored in separate electronic files and merged with the primary data as needed. The following data quality control methods will be used: single entry with random checks of accuracy, range checks, testing of database by study team prior to moving to data analysis, and regular, periodic extraction and cleaning of data.

14.0 Privacy/Confidentiality Issues

Confidentiality will be protected by ensuring all research staff have been properly trained in confidentiality and human subject research procedures, coding all subject information when possible, and by securing subject files in a locked filing cabinet or on secured databases with access available only to the study physicians and research staff. Furthermore, data entered into a computer database will only use subject codes on secured computers that will be password protected with access available only to the study physicians and research staff. Limited screening information (first name, phone number) obtained from potential research subjects who subsequently do not participate in the research study will be held for 6 months and then destroyed.

15.0 Follow-up and Record Retention

Paper copies of medical records and source documentation will be kept for seven years after the study is closed with the IRB. One year after study closure, the documents will

be shipped to the Indiana University Department of Psychiatry long-term storage facility until destruction.

